1.9.2 Safety Analysis

The Safety population will be used for analyses of each of the safety endpoints. All concomitant medications will be tabulated according to drug class and preferred term using the WHO dictionary. Clinical laboratory tests, vital signs, physical examinations and ECG will be summarized by number of patients, frequency rates and number of events by adverse events and by treatment group. The time point of each event will

also be summarized. C-SSRS results will be summarized by mean values and changes from baseline at each visit.

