1.9.1 Efficacy Analysis

Analysis of primary and secondary efficacy endpoints will be performed on the mITT, and PP populations.

The primary efficacy hypothesis is that treatment with one or both of the T-817MA doses will result in a statistically significant reduction in total ADAS-cog score relative to the placebo group at Week 52 in the mITT population. The first stage in the hierarchical analysis will test the statistical hypothesis of no difference between the three treatment groups.

A hierarchical strategy will be used to preserve alpha: the primary analysis will first compare the high dose arm to placebo at an alpha level of 0.05, and if this is positive the low dose group will be compared to placebo again at an alpha level of 0.05.

The first stage in the hierarchical analysis will test the statistical hypothesis of no difference between the three treatment groups.

Categorical variables will be summarized by treatment group using frequency distribution: number of non-missing observations (N) and percentages (%). Percentages will be calculated within each treatment group on the number of non-missing observations. Continuous variables will be summarized using standard quantitative statistics: number of non-missing observations (N), mean, standard deviation (SD), median and range (minimum and maximum observed values).

OC and Imputation analysis of primary and secondary efficacy endpoints (the change in ADAS-cog and MMSE from Baseline to Weeks 12, 24, 36, 44, 52 and 56, the change in ADCS-ADL, FAQ and NPI from Baseline to Weeks 12, 24, 36 and 52 and the change in ADCS-CGIC from Baseline to Weeks 12, 24, 36, 44 and 52) will be performed in the mITT and PP populations.

Subgroup analysis (e.g. gender, age, baseline MMSE score) will be performed in the mITT and PP populations.

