1.9.2.1 Adverse Events

Adverse events (AE) occurring after the start of study drug dosing at Baseline (Week 0) will be summarized descriptively for the safety population. All AEs will be coded according to system organ class (SOC) and preferred term (PT) using a Medical Dictionary for Regulatory Activities (MedDRA) dictionary. Summary tables showing the number of patients and percent within each category will be generated for each of the following types of adverse events and its relationship to study treatment (related to study treatment):

- All events
- Serious events
- Deaths
- Events leading to withdrawal
- Severe events

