1.9.2.2 Laboratory parameters

Laboratory parameters will be summarized by visit. Frequencies of high and low values with respect to the normal range will be displayed, as will shift tables comparing each treatment visit (Weeks 4, 8, 12, 18, 24, 30, 36, 44, 52 and 56) and Baseline visit by time point and treatment group. Urinalysis values will be cross-summarized at pre-dose and post-dose.

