1.9.2.3 Other Safety Parameters

Vital signs and ECG parameters will be summarized across groups by visit using descriptive statistics, and at each outcome visit and at end of study.

Physical examination findings and ECG abnormalities and number of patients will be summarized as the count and percentage of patients by eCRF pre-defined categories at last visit. Change from baseline at last visit will be summarized in a shift table crossing baseline and last visit results. Concomitant medications will be summarized by treatment group, drug class and preferred term. Vital signs will be summarized by visit using descriptive statistics.

The change in the C-SSRS Ped score from Baseline to Weeks 12, 24, 36 and 52 will be summarized between each T-817MA treatment group (high dose and low dose) and the placebo treatment group.

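### The C-SSRS, a named safety endpoint, is summarised only by means and changes in an undefined score; a patient count and a shift table should be added

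*Combined protocol and SAP*

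**What the plan says.** The C-SSRS Pediatric is listed as a safety measure in the synopsis (Secondary Endpoints) and again in section 1.8. Two sentences say how it will be reported:

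- Section 1.9.2: "C-SSRS results will be summarized by mean values and changes from baseline at each visit".
- Section 1.9.2.3: "The change in the C-SSRS Ped score from Baseline to Weeks 12, 24, 36 and 52 will be summarized", for each active dose group and placebo. The score is not defined and no statistic is named.

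Other safety measures get some categorical treatment:

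- Laboratory values (section 1.9.2.2): "Frequencies of high and low values with respect to the normal range will be displayed, as will shift tables comparing each treatment visit".
- Physical examination findings and ECG abnormalities (section 1.9.2.3): counts and percentages at the last visit, followed by "Change from baseline at last visit will be summarized in a shift table crossing baseline and last visit results".
- Adverse events (section 1.9.2.1): "Summary tables showing the number of patients and percent within each category will be generated".

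The document is titled a synopsis, and section 1.9 leaves full analysis detail to a separate SAP.

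**The concern.** For a suicidality assessment, a safety reader mainly wants to know how many patients in each arm had a positive result after baseline and how many got worse. A mean does not answer that. If most patients score zero, a few affected patients barely move it, and one patient's improvement can cancel another's worsening. Reported only as written here, the endpoint could look flat in every arm while the number of affected patients differed, unless those patients also appeared in the adverse event tables.

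**Working it through.** **Text check.** The documents contain no C-SSRS figure to reproduce, so the first step is to compare how each measure is summarised.

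| Measure | Section | Categorical summary stated? |
|---|---|---|
| Adverse events | 1.9.2.1 | Yes: patients and percent |
| Laboratory values | 1.9.2.2 | Yes: high/low frequencies and shift tables |
| Physical examination, ECG findings | 1.9.2.3 | Yes: count, percentage, shift table at last visit |
| C-SSRS | 1.9.2, 1.9.2.3 | No: means and changes in a score |

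**Illustration of what a mean can hide.**

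Inputs:
- Arm size n = 150, from section 1.1 (at least 450 randomised, 450/3 = 150). This agrees with the plan's own inflation for dropout: 110/(1 − 0.26) = 148.6, or 149, which the plan takes as 150.
- Assumed, because the documents describe neither the instrument nor its scoring: k patients move from 0 to a score s, with k and s each between 1 and 5, and everyone else stays at 0.

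Formulas: mean change m = k × s / n; SD = √{[k(s − m)² + (n − k)m²]/(n − 1)}.

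| k (percent of 150) | s | m | SD |
|---|---|---|---|
| 1 (0.7%) | 1 | 1/150 = 0.007 | 0.08 |
| 1 (0.7%) | 5 | 5/150 = 0.033 | 0.41 |
| 5 (3.3%) | 1 | 5/150 = 0.033 | 0.18 |
| 3 (2.0%) | 5 | 15/150 = 0.100 | 0.70 |
| 5 (3.3%) | 3 | 15/150 = 0.100 | 0.54 |
| 5 (3.3%) | 5 | 25/150 = 0.167 | 0.90 |

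1. Over the assumed range the mean change runs from 0.007 to 0.167.
2. The mean fixes only the product k × s. A mean of 0.033 fits one patient rising by 5 or five patients rising by 1. A mean of 0.100 fits three patients or five.
3. Changes can cancel. If five patients worsen by 3 and five with a non-zero baseline improve by 3, the mean change is (5 × 3 − 5 × 3)/150 = 0, the same as in an arm where nobody changed. A shift table would show five worsened (3.3%) and five improved.
4. Dropout does not alter this. With 26% lost, n = 150 × 0.74 = 111 at Week 52, and the range becomes 1/111 = 0.009 to 25/111 = 0.225. The ambiguity between k and s is the same.

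The SD would separate some of these pairs, but neither C-SSRS sentence promises one.

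**The case against.** Several objections have weight.

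- **Detail is deferred.** This is a synopsis, and the tables asked for are the sort of detail that section 1.9 leaves to the separate SAP. A reader might infer that the trial has no such count. The documents do not support that, because the SAP was not available. The point that stands is narrower: the synopsis does name a method for this endpoint, and that method is not enough on its own.
- **Adverse event tables are a backstop.** A positive assessment reported as an adverse event is counted under section 1.9.2.1. This limits the gap but does not close it, because no section links C-SSRS responses to adverse event reporting.
- **General descriptive rules exist.** Section 1.9.1 says "Categorical variables will be summarized by treatment group using frequency distribution: number of non-missing observations (N) and percentages" and "Continuous variables will be summarized using standard quantitative statistics: number of non-missing observations (N), mean, standard deviation (SD), median and range". These sit under efficacy and do not name the C-SSRS, so they cannot be relied on to supply a count or an SD for it.
- **The wording leaves room.** The text does not say that changes will be summarised only as means. A categorical change summary is not excluded, but none is stated.
- **The instrument is not described.** The documents do not set out its items or scoring. The categories proposed below assume that ideation and behaviour responses are recorded separately.

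Three stronger readings are tempting and should not be drawn:

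- Section 1.9.2 also says "Clinical laboratory tests, vital signs, physical examinations and ECG will be summarized by number of patients, frequency rates and number of events", and a reader might infer that the C-SSRS was singled out for weaker treatment in that paragraph. The sentence goes on to tie those counts to adverse events, so it is poor evidence of that.
- A reader might object that by-visit output cannot show how many distinct patients were ever affected. That is true, but the by-visit laboratory, vital sign and ECG summaries share the limit. It is not a defect peculiar to the C-SSRS.
- A reader might see a contradiction between reporting at every visit (section 1.9.2) and at Weeks 12, 24, 36 and 52 (section 1.9.2.3). The first can mean every visit at which the C-SSRS is given, so this is a wording point only.

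**Conclusion.** The concern holds in a limited form. On the stated text, a named safety endpoint is reported by means and changes in an undefined score. A reader could not tell how many patients per arm had a positive or worsened result, except through adverse event reports. The size cannot be given as an event rate, because the documents supply no C-SSRS data. The illustration shows only that, with 1 to 5 of 150 patients affected (0.7% to 3.3%), the mean change would lie between 0.007 and 0.167 and would not identify the count. It rests on the assumption that most patients score zero and on the assumed scores. Efficacy and sample size are untouched. This is an optional but cheap improvement, not an error that threatens the trial's conclusions.

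**What to change.** In sections 1.9.2 and 1.9.2.3, keep the means if wanted and add, for each arm in the Safety population:

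1. number and percentage of patients with any post-baseline suicidal ideation;
2. number and percentage with any post-baseline suicidal behaviour;
3. number and percentage with new or worsened status relative to baseline;
4. a shift table from baseline to the worst post-baseline result.

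Define the score if means are retained, and describe the C-SSRS visits in the same way in both sections, using the visits at which it is already collected. If the separate SAP already contains these tables, align the synopsis wording with it.

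The cost is wording in two sections and a few extra tables. No new assessments are needed, provided the individual item responses are recorded, which the documents do not say.

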1.9.2.1 Adverse Events

Adverse events (AE) occurring after the start of study drug dosing at Baseline (Week 0) will be summarized descriptively for the safety population. All AEs will be coded according to system organ class (SOC) and preferred term (PT) using a Medical Dictionary for Regulatory Activities (MedDRA) dictionary. Summary tables showing the number of patients and percent within each category will be generated for each of the following types of adverse events and its relationship to study treatment (related to study treatment):

- All events
- Serious events
- Deaths
- Events leading to withdrawal
- Severe events

1.9.2.2 Laboratory parameters

Laboratory parameters will be summarized by visit. Frequencies of high and low values with respect to the normal range will be displayed, as will shift tables comparing each treatment visit (Weeks 4, 8, 12, 18, 24, 30, 36, 44, 52 and 56) and Baseline visit by time point and treatment group. Urinalysis values will be cross-summarized at pre-dose and post-dose.

1.9.2.3 Other Safety Parameters

Vital signs and ECG parameters will be summarized across groups by visit using descriptive statistics, and at each outcome visit and at end of study.

Physical examination findings and ECG abnormalities and number of patients will be summarized as the count and percentage of patients by eCRF pre-defined categories at last visit. Change from baseline at last visit will be summarized in a shift table crossing baseline and last visit results. Concomitant medications will be summarized by treatment group, drug class and preferred term. Vital signs will be summarized by visit using descriptive statistics.

The change in the C-SSRS Ped score from Baseline to Weeks 12, 24, 36 and 52 will be summarized between each T-817MA treatment group (high dose and low dose) and the placebo treatment group.

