A Phase 2 multi-center, randomized, double blind, placebo-controlled, parallel group study to evaluate the efficacy and safety of T-817MA in patients with mild to moderate Alzheimer's Disease (US202)

Protocol & SAP Synopsis

2018.7.12

NCT02079909

PROTOCOL TITLE	A Phase 2 multi-center, randomized, double blind, placebo-controlled, parallel group study to evaluate the efficacy and safety of T-817MA in patients with mild to moderate Alzheimer's Disease (US202)
STUDY SPONSOR	Toyama Chemical Co., Ltd.
COORDINATING CENTER	Alzheimer's Disease Cooperative Study (ADCS)
STUDY PHASE	2
INDICATION	For the treatment of mild to moderate Alzheimer's disease.
OBJECTIVES	
The primary objective is to evaluate the efficacy of T-817MA as measured by ADAS-cog and ADCS-CGIC.
 
The secondary objectives are:
 
 • To evaluate the safety and tolerability of T-817MA measured by clinical safety laboratories, physical examinations, ECGs and solicitation of adverse events. • To evaluate the efficacy of T-817MA as measured by ADCS-ADL, FAQ, Neuropsychiatric Inventory (NPI) and Mini-mental State Examination (MMSE).
ADDITIONAL OBJECTIVES	Population pharmacokinetics of T-817 will be analyzed. Volumetric MRI (vMRI) scans will be evaluated. CSF biomarkers will be evaluated in a subset of the study population.
PRIMARY ENDPOINTS	The change in the ADAS-cog and ADCS-CGIC from Baseline to Week 52 between each T-817MA treatment group (high or low dose) and the placebo group.
SECONDARY ENDPOINTS	
 • The change in the ADAS-cog from Baseline to Weeks 12, 24, 36, 44 and 56. • The change in the ADCS-CGIC from Baseline to Weeks 12, 24, 36 and 44. • The change in the MMSE from Baseline to Weeks 12, 24,

	
36, 44, 52 and 56.
 
 • The change in the ADCS-ADL, FAQ and NPI from Baseline to Weeks 12, 24, 36 and 52. • Safety as measured by occurrence of adverse events, clinical laboratory tests, vital signs, physical examinations, ECGs, use of concomitant medications, and the C-SSRS Pediatric.

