DRUG DOSAGE AND FORMULATION	
Two dosing levels of T-817MA (224 and 448 mg/day) or placebo. The 448 mg dose arm will be started at 224 mg for 4 weeks, and then increased to 448 mg.
 
Film-coated tablets are 112 mg T-817MA or placebo and dispensed in blister packs.
 
The study medication will be taken once daily after breakfast.

ROUTE OF ADMINISTRATION	Oral
TREATMENT DURATION	Duration of treatment is 52 weeks. There is also a screening period of up to 6 weeks; and a 4-week post-treatment observation period. Each patient may participate in the study for up to 62 weeks.
PROCEDURES	
Physical examinations, cognitive and functional test batteries, clinical and research venipunctures, volumetric MRIs, and lumbar puncture in a subset of patients.
 
Visits: Screening (within 42 days prior to randomization),

	Baseline (Week 0), Weeks 4, 8, 12, 18, 24, 30, 36, 44, 52, and 56 (follow-up)
--	---

STATISTICAL METHODS

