1.5.2 Secondary Efficacy Endpoints

1. The change in the following assessments from Baseline to Week 52 between each T-817MA treatment group (high dose and low dose) and the placebo treatment group in the mITT population:
 - a. ADCS-ADL
 - b. FAQ
 - c. NPI

d. MMSE

A Mixed-effects Model Repeated Measure will be used to calculate differences at 52 weeks, using baseline assessment as a covariate.

2. The following will also be analyzed in the mITT population:
 - a. The change in ADAS-cog, ADCS-CGIC, ADCS-ADL, FAQ, NPI and MMSE from Baseline to Weeks 12, 24 and 36
 - b. The change in ADAS-cog, ADCS-CGIC and MMSE from Baseline to Week 44
 - c. The change in ADAS-cog and MMSE from Baseline to Week 56
3. Primary and secondary endpoints will similarly be assessed in the per-protocol population.

1.6 vMRI

Observed Case analysis for differences in change of vMRI over 52 weeks with mITT and PP.

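### The category counts and the only named shift table for ECG abnormalities and physical examination findings rest on one undefined last visit, so on-treatment changes that resolve by then can be missing from those tables

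*Combined protocol and SAP*

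**What the plan says.** The secondary safety objective is to be "measured by clinical safety laboratories, physical examinations, ECGs and solicitation of adverse events", so ECG and physical examination stand beside laboratory tests and adverse events as named measures.

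Section 1.9.2.3 sets the summaries for these two:

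- Physical examination findings and ECG abnormalities "will be summarized as the count and percentage of patients by eCRF pre-defined categories at last visit".
- The one shift table named for them is tied to that same time point: "Change from baseline at last visit will be summarized in a shift table crossing baseline and last visit results".
- For ECG (and vital signs), "ECG parameters will be summarized across groups by visit using descriptive statistics, and at each outcome visit and at end of study".

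The synopsis does not define the last visit, and Section 1.9.2.3 also uses the term end of study without saying whether the two coincide.

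Three other places bear on the point. Section 1.9.2 promises patient numbers, frequency rates and event counts for ECG and physical examination among other data, arranged by adverse event and treatment group, and adds that the timing of events will be summarised. Section 1.9.2.2 gives laboratory data high and low frequencies and a shift table against baseline at each of ten listed weeks. Section 1.9 leaves the full detail of the safety analyses to a separate SAP.

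**The concern.** A table taken at one visit per patient shows the state at that visit, not what happened during treatment. An ECG category that becomes abnormal in mid-treatment and returns to normal by the chosen visit appears as no change. Whether that patient is counted anywhere else then depends on how Section 1.9.2 is read, or on someone having reported the finding as an adverse event.

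The undefined term adds a second problem. The Treatment Duration row describes "a 4-week post-treatment observation period", and Week 56 is the final scheduled visit. If the last visit is Week 56, the tables describe completers off treatment. If it is each patient's last observed visit, completers and early leavers are mixed at different lengths of exposure.

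What is at stake is how fully a stated safety objective is reported. No efficacy conclusion, alpha or power is involved.

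**Working it through.** The plan gives no figure to reproduce here. The check is a count of visits and a side-by-side reading of the sections.

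**Visits.** The Procedures row lists post-baseline visits at Weeks 4, 8, 12, 18, 24, 30, 36, 44, 52 and 56, which is 10. Treatment lasts 52 weeks, so 9 visits fall in the treatment period and 1 falls 56 − 52 = 4 weeks after it. Section 1.9.2.2 lists Week 56 among the treatment visits, so the plan's own terms do not separate on-treatment from follow-up.

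**On-treatment assessments that reach the last-visit tables, for a completer.** No ECG or physical examination schedule is supplied, so three schedules are shown. The second borrows the C-SSRS weeks ("The change in the C-SSRS Ped score from Baseline to Weeks 12, 24, 36 and 52 will be summarized") purely as an example of a sparser one.

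| Assumed on-treatment schedule | Last visit = Week 52 | Last visit = Week 56 (if assessed then) |
|---|---|---|
| All 9 visits | 1 of 9 used; 8/9 = 89% unused | 0 of 9 used |
| Weeks 12, 24, 36, 52 | 1 of 4 used; 3/4 = 75% unused | 0 of 4 used |
| Week 52 only | 1 of 1 used; no gap | 0 of 1 used |

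Under the last-observed reading, a completer falls in one column or the other, depending on whether the assessment is made at Week 56.

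**Early leavers.** At the planned 26% dropout, 0.26 × 150 = 39 patients per arm and 0.26 × 450 = 117 overall leave before the end of treatment. Under the last-observed reading they enter the tables at varying exposure. Under a fixed-week reading they may have no entry. This is the number for whom the definition matters most; it is not a count of errors.

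**Is there more than one assessment?** The Study Design row says safety is evaluated at every visit, and a by-visit ECG summary implies repeated ECGs. Neither confirms which instruments are used at which visit. Not everything runs to Week 56: the C-SSRS change stops at Week 52, and the efficacy item for Week 56 is "The change in ADAS-cog and MMSE from Baseline to Week 56", with no other scale. Week 56 is therefore a possible reading of the last visit, not an established one.

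**What each data type gets in this synopsis.**

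| Data | By-visit summary | Categorical patient count | Shift from baseline |
|---|---|---|---|
| Laboratory | Yes | High/low frequencies | Each of 10 visits |
| ECG | Parameters, descriptive statistics | Last visit; others only through Section 1.9.2 | Last visit |
| Physical examination | None named | Last visit; others only through Section 1.9.2 | Last visit |

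The by-visit ECG statistics can show that a group has moved. They name no count of patients with an abnormality.

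**The case against.** The strongest reply is Section 1.9.2. It names ECG and physical examination, promises numbers of patients and events, is not limited to a last visit, and says event timing will be summarised. On a broad reading, transient abnormalities are counted there by patient and time point, and the gap narrows to the shift table. On a narrow reading, its arrangement by adverse event confines it to findings reported as such. The wording does not settle which is meant. A reader might infer from Section 1.9.2.3 alone that transient findings go uncounted altogether; Section 1.9.2 and the by-visit ECG summary do not allow that conclusion.

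The document is also a synopsis, and Section 1.9 defers detail to a separate SAP that may define the visit and add the tables. It would be wrong to infer that the trial's full plan lacks them. That reply does not remove the point, because on these data the synopsis is not silent: it states a rule, and the rule is a single visit.

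Finally, a last-visit shift table is a legitimate descriptive summary, and nothing obliges ECG and physical examination to copy the laboratory layout. That stands. It argues for keeping the existing table and adding to it.

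**Conclusion.** The point holds as a minor one about how safety data are specified. In this synopsis the category counts in Section 1.9.2.3 and the only shift table named for ECG abnormalities and physical examination findings use one undefined visit. Provided that these assessments are made at more than one post-baseline visit, on-treatment changes that resolve by then are missing from those tables. Section 1.9.2 leaves unclear whether such findings are counted elsewhere when they are not reported as adverse events.

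The number of patients affected cannot be determined: the documents give no rate of abnormality, resolution or adverse event reporting, and no assessment schedule. If Week 52 is both the only post-baseline assessment and the last visit, completers have no gap. Two stronger inferences should be resisted: that the tables are certainly off treatment, since Week 56 is only one of three possible readings, and that the 39 early leavers per arm are misreported. Confidence is limited by the absence of the separate SAP and of a schedule for these assessments.

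**What to change.** - In Section 1.9.2.3, define the last visit as the last on-treatment assessment, and say how it relates to end of study.
- Add the number and percent of patients in each arm with any treatment-emergent ECG abnormality, and likewise for physical examination findings, over all on-treatment assessments. State what counts as treatment-emergent when the finding was already present at baseline.
- Add a baseline-to-worst shift table over the same assessments, stating how the eCRF categories are ordered. Keep the last-visit table beside it.
- Report any Week 56 findings separately as post-treatment.
- In Section 1.9.2, say whether the patient and event counts for ECG and physical examination cover all abnormal findings or only those reported as adverse events.
- Align both sections with the separate SAP. If it already contains these tables, only the synopsis wording needs to change.

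The cost is some wording and a few extra descriptive tables from data already planned. No visits or patients are added.
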